3.2. Justification for Study Design

A randomized, double-blind, parallel-group design is appropriate given the objectives of this study.

The dosing regimen planned for this study is consistent with the dosing regimen in the pivotal efficacy studies.

In order to blind the treatment groups based on both dose-volume and number of injections, each patient will receive three 1.5-mL sc injections (three 1.5-mL sc injections of active drug, one 1.5-mL sc injection of active drug and two 1.5-mL injections of placebo, or three 1.5-mL injections of placebo) at visits 2, 5, 8, and 11. See Section 5.1 for additional details.

3.3. Primary and Secondary Efficacy Measures and Time Points

All efficacy measures are exploratory.

3.3.1. Primary Efficacy Measure and Time Points

There is no primary efficacy measure.

3.3.2. Secondary Efficacy Measures and Time Points

There are no secondary efficacy measures.

3.4. Safety and Tolerability Measures and Time Points

Safety and tolerability will be assessed at time points specified in Table 1 (patients rolling over from the pivotal efficacy studies), Table 2 (patients not rolling over from the pivotal efficacy studies), and Table 3 (patients rolling over from the pivotal efficacy studies for ADA assessment only) using the following measures, as applicable:

- inquiries about adverse events
- inquiries about concomitant medication usage
- vital signs measurements (systolic and diastolic blood pressure, pulse, temperature, and respiratory rate)
- 12-lead ECGs
- physical examination, including weight
- safety laboratory tests (serum chemistry, hematology, coagulation, and urinalysis)
- serum/urine beta-human chorionic gonadotropin (β -HCG) tests (women of childbearing potential only)
- injection site reaction (ie, erythema, induration, ecchymosis, and pain) assessments
- eC-SSRS

A description of the safety measures is provided in Section 7.

3.5. Pharmacokinetic/Immunogenicity/Biomarker Measures and Time Points

A description of the pharmacokinetic, biomarker, and immunogenicity measures is provided in Section 8.

3.5.1. Pharmacokinetic Measures and Time Points

Blood samples for pharmacokinetic analysis of TEV-48125 will be collected from all patients for the purpose of pharmacokinetic/pharmacodynamic relationship assessment at time points specified in Table 1 (patients rolling over from the pivotal efficacy studies) and Table 2 (patients not rolling over from the pivotal efficacy studies). The pharmacodynamic parameters will be the efficacy responses.

The actual date and time of each blood sample, as well as the date and time of the last study drug dose prior to each sample, will be recorded in the case report form (CRF).

3.5.2. Immunogenicity Measures and Time Points

Blood samples for immunogenicity analysis will be collected at time points specified in Table 1 (patients rolling over from the pivotal efficacy studies), Table 2 (patients not rolling over from the pivotal efficacy studies), and Table 3 (patients rolling over from the pivotal efficacy studies for ADA assessment only).

3.5.3. Biomarker Measures and Time Points

Biomarker blood and urine samples will be collected at time points specified in Table 1 (patients rolling over from the pivotal efficacy studies) and Table 2 (patients not rolling over from the pivotal efficacy studies).

A blood sample for pharmacogenomic analysis will be collected from patients who consent to pharmacogenomic analysis and who have not already had a sample collected during the pivotal efficacy studies at the baseline visit or any visit thereafter.

3.6. Exploratory Measures and Time Points

Efficacy will be assessed at time points specified in Table 1 (patients rolling over from the pivotal efficacy studies) and Table 2 (patients not rolling over from the pivotal efficacy studies) using the following exploratory efficacy measures:

- exploratory efficacy endpoints derived from headache data (ie, occurrence of headache, duration of headache, maximum severity of headache, and acute migraine-specific medication use), which will be collected using an electronic headache diary device
- HIT-6 (patients with CM only)
- MIDAS questionnaire (patients with EM only)
- PHQ-2/PHQ-9 (Note: Patients will first respond to the PHQ-2. They will respond to questions 3 through 9 [unique questions] of the PHQ-9 only if the PHQ-2 is positive.)
- MSQOL questionnaire

- EQ-5D-5L questionnaire
- PGIC scale
- WPAI questionnaire

A description of the efficacy measures is provided in Section 6.

3.7. Randomization and Blinding

The sponsor, investigators, study staff (except for staff involved in bioanalytical analyses), and patients will be blinded to treatment assignment. The Sponsor will be unblinded when the pivotal efficacy studies have been unblinded. A computer-generated master randomization list will be provided to drug packaging facilities. Packaging vendor(s) will package study drug into kits according to Good Manufacturing Practice procedures. Kits will be identical in appearance, and will contain 1 prefilled syringe with active drug or placebo. Adequate kit supply for upcoming study visits will be managed by interactive response technology (IRT) and kept (refrigerated at 2°C to 8°C) on site.

Patients will be stratified by gender, country, and baseline preventive medication use (yes, no) during the pivotal efficacy studies or this study if they are not rolling over from the pivotal efficacy study.

Patients rolling over from the pivotal efficacy studies who were randomized to the active treatment groups will continue receiving the same treatment throughout the study. Patients rolling over from the pivotal efficacy studies who received placebo and patients not rolling over will be randomly assigned in a 1:1 ratio to receive quarterly TEV-48125 at 675 mg or monthly TEV-48125 at 225 mg (Note: Patients with CM will receive a 675-mg loading dosing at visit 2 and TEV-48125 at 225 mg at each subsequent visit.).

The IRT will manage initial drug supply, maintenance of adequate study drug supplies on site, and study randomization centrally. At the time of each study visit, the IRT will be queried, and site personnel will retrieve and administer a 1.5-mL volume from each syringe contained in the appropriately numbered kit(s).

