Method of Blinding and Randomization: The sponsor, investigators, study staff (except for staff involved in bioanalytical analyses), and patients will be blinded to treatment assignment. A computer-generated master randomization list will be provided to drug packaging facilities. Packaging vendor(s) will package study drug into kits according to Good Manufacturing Practice procedures. Kits will be identical in appearance and contain a prefilled syringe with active drug or placebo.

Patients will be stratified by gender, country, and baseline preventive medication use (yes, no) during the pivotal efficacy studies or this study if they are not rolling over from the pivotal efficacy study.

Patients rolling over from the pivotal efficacy studies who were randomized to the active treatment groups will continue receiving the same treatment throughout this study. Patients rolling over from the pivotal efficacy studies who received placebo and patients not rolling over from the pivotal efficacy studies will be randomly assigned in a 1:1 ratio to receive quarterly TEV-48125 at 675 mg or monthly TEV-48125 at 225 mg (Note: Patients with CM will receive a 675-mg loading dosing at visit 2 and TEV-48125 at 225 mg at each subsequent visit.).

The interactive response technology (IRT) will manage initial drug supply, maintenance of adequate study drug supplies on site, and study randomization centrally. At the time of each study visit, the IRT will be queried, and site personnel will retrieve and administer a 1.5-mL volume from each syringe contained in the appropriately numbered kit(s).

Study Drug Dose, Mode of Administration, and Administration Rate: Prefilled syringes (active or placebo) will be contained in uniquely numbered kits and stored (refrigerated at 2°C to 8°C) on site. Active syringes will contain 150 mg/mL of TEV-48125, and placebo syringes will contain the same vehicle and excipients as those for active injections. Each kit will contain 1 prefilled syringe.

Study drug will be administered by qualified study personnel as sc injections approximately every 4 weeks (28 days). In order to maintain the study blind, all patients will receive 3 injections at visits 2, 5, 8, and 11 and 1 injection at all other visits as detailed in the table below.

Summary of Study Drug Administration

Treatment group in this study	Visit 2	Visits 5, 8, and 11	Visits 3, 4, 6, 7, 9, 10, 12, and 13

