3.8.2. Blinding/Unblinding

Pharmacokinetic data may be assessed during the study. Personnel responsible for bioanalysis will be provided with the randomization code in order to facilitate the analysis. However, the personnel responsible for bioanalysis will not have access to clinical safety and efficacy data and will provide concentration data to other personnel in a manner that will not identify individual patients (ie, a dummy patient identifier will be linked to an individual patient's concentration data).

For information about personnel who may be aware of treatment assignments, see Section 3.7. These individuals will not be involved in conduct of any study procedures or assessment of any adverse events.

In case of a serious adverse event or pregnancy, or in cases when knowledge of the study drug assignment is needed to make treatment decisions, the investigator may unblind the patient's drug assignment as deemed necessary, mainly in emergency situations. Individual treatment codes, indicating the treatment randomization for each randomized patient, will be available to the investigator(s) and/or pharmacist(s) at the study center via the IRT, both via telephone and internet. If possible, the sponsor should be notified of the event prior to breaking of the code. If this is not possible, the sponsor should be notified immediately afterwards, and the patient's drug code assignment should not be revealed. Breaking of the treatment code can always be performed by the site without prior approval by the sponsor.

When a blind is broken, the patient will be withdrawn from the study, and the event will be recorded onto the CRF. The circumstances leading to the breaking of the code should be fully documented in the investigator's study files and in the patient's source documentation. Treatment assignment should not be recorded in any study documents or source documents.

In blinded studies, for adverse events that are defined as suspected unexpected serious adverse reaction (SUSAR) (ie, reasonable possibility; see Section 7.1.4), Global Patient Safety & Pharmacovigilance may independently request that the treatment code be revealed (on a case-by-case basis) to comply with regulatory requirements. The report will be provided in an unblinded manner for regulatory submission. If this occurs, blinding will be maintained for the investigator and for other personnel involved in the conduct, analysis, and reporting of the data.

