7.1.5.2. Expectedness

A serious adverse event that is not included in the Adverse Reaction section of the relevant reference safety information by its specificity, severity, outcome, or frequency is considered an unexpected adverse event. The reference safety information for this study is the Investigator's Brochure.

The sponsor's Pharmacovigilance Department will determine the expectedness for all serious adverse events.

For the purpose of SUSAR reporting, the version of the reference safety information document at the moment of the occurrence of the SUSAR applies.

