Each report of a serious adverse event will be reviewed and evaluated by the investigator and the sponsor to assess the nature of the event and the relationship of the event to the study drug, study procedures, and underlying disease.

Additional information (follow-up) about any serious adverse event unavailable at the initial reporting should be forwarded by the investigational center within 24 hours of when it becomes known to the same address as the initial report.

For all countries, the sponsor's Global Patient Safety & Pharmacovigilance Department will distribute the Council for International Organizations of Medical Sciences form/extensible markup language file to the LSO and/or CRO for local submission to the regulatory authorities, IEC/IRBs, and investigators, according to regulations. The investigator is responsible for ensuring that the IRB/IEC is also informed of the event, in accordance with local regulations.

Blinding will be maintained for the people who are involved directly in the study. Therefore, in case of a SUSAR, only the LSO and/or CRO personnel involved with safety regulatory submissions will receive the unblinded report for regulatory submission; the others will receive a blinded report.

Note: Although pregnancy is not a serious adverse event, the process for reporting a pregnancy is the same as that for reporting a serious adverse event, but using the pregnancy form (see Section 7.2).

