7.11. Methods and Timing of Assessing, Recording, and Analyzing Safety Data

All adverse events will be reviewed on a periodic basis by the clinical project physician/medical monitor according to the safety monitoring plan (eg, scheduled safety reviews for TEV-48125) as interim/preliminary safety databases become available. Safety data will additionally be evaluated periodically and ad hoc (if necessary) in the Product Safety Group.

Methods and timing of assessing safety data are discussed in Section 3.14. Procedures for recording safety data are discussed in Section 13.1, and methods of safety analyses are discussed in Section 9.7.2.

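### Unblinding the whole sponsor at pivotal unblinding contradicts the synopsis and the Section 3.8.2 assurance, because sponsor staff assess adverse events in this study

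*Protocol*

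**What the plan says.** Four places in the current text deal with the sponsor's blind.

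- **Protocol synopsis, Method of Blinding and Randomization:** "The sponsor, investigators, study staff (except for staff involved in bioanalytical analyses), and patients will be blinded to treatment assignment". No trigger ends this.
- **Protocol 3.7:** the same opening statement, followed by "The Sponsor will be unblinded when the pivotal efficacy studies have been unblinded". No team, role or set of codes is specified.
- **Protocol 3.8.2:** "For information about personnel who may be aware of treatment assignments, see Section 3.7", and then "These individuals will not be involved in conduct of any study procedures or assessment of any adverse events".
- **SAP 2.4.2:** repeats both the unblinding sentence from 3.7 and the assurance from 3.8.2.

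Other sections give adverse-event work to the sponsor:

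- 7.1.5.3.1: "Each report of a serious adverse event will be reviewed and evaluated by the investigator and the sponsor", covering both its nature and its relationship to study drug.
- 7.1.5.2: "The sponsor's Pharmacovigilance Department will determine the expectedness for all serious adverse events".
- 7.11: "All adverse events will be reviewed on a periodic basis by the clinical project physician/medical monitor according to the safety monitoring plan".
- 3.12: the sponsor may withdraw a patient at any time, with adverse events among the listed reasons.
- 11.1.2: the sponsor decides whether a protocol violator continues.

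Section 3.8.3 states that a data monitoring committee is not applicable.

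**The concern.** Section 3.8.2 defines the people who may know treatment by pointing to 3.7, and 3.7 names the sponsor without limit. Those people are then said to have no part in assessing adverse events. The protocol gives several such tasks to the sponsor, so once the pivotal studies are unblinded the two statements cannot both be true. The synopsis statement fails at the same moment.

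The primary endpoints are safety endpoints (Protocol 9.5.1 and 9.7.1). At stake are the sponsor's own judgements: causality of serious adverse events, expectedness, medical monitoring, and decisions to withdraw or retain patients. People who know the regimen could make these, while the study documents assure the reader that they do not. No independent committee stands between those judgements and the data.

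**Working it through.** **1. The passages side by side after pivotal unblinding**

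| Statement | Place | Sponsor's position |
|---|---|---|
| Sponsor blinded, no end point | Synopsis | Blinded |
| Sponsor unblinded at pivotal unblinding | Protocol 3.7, SAP 2.4.2 | Unblinded, no limit |
| People aware of assignment (see 3.7) do not assess adverse events | Protocol 3.8.2, SAP 2.4.2 | Barred from assessment |
| Sponsor evaluates serious events, judges expectedness, reviews all events | Protocol 7.1.5.3.1, 7.1.5.2, 7.11 | Assessing |

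Rows 1 and 2 conflict. So do rows 2, 3 and 4 taken together. The SAP preface says that the SAP prevails over the protocol where they differ. That favours row 2 over row 1, but it cannot settle rows 2 and 3, because SAP 2.4.2 contains both.

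**2. Does the event fall inside the study?**

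The planned schedule reproduces: dose 12 is at 11 × 28 = day 308, end of treatment at 308 + 28 = day 336, and the final visit at 308 + 225 = day 533. Under Protocol 3.1, visit 2 may fall on the pivotal end-of-treatment day, so a late rollover can have all 336 treatment days ahead when pivotal treatment ends. Protocol 9.12 plans an interim cut of this study after pivotal database lock, so the study is expected to be running then.

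No unblinding date is given. As an illustration only, suppose it comes 1, 3 or 6 months (30.4-day months) after the last rollover's first dose. That patient would have 336 − 30 = 306, 336 − 91 = 245 or 336 − 182 = 154 treatment days left. Earlier entrants would have fewer.

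**3. How many patients would pivotal codes alone disclose?**

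Planned enrolment reproduces: 867 + 675 + 300 = 1842. Rollovers are 867 + 675 = 1542, which is 1542/1842 = 83.7%. Active rollovers stay on their pivotal regimen, so their pivotal code is their current treatment. The pivotal allocation and the rollover rate are not stated. Assuming full rollover:

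| Assumed share on active drug | Patients | Share of 1842 |
|---|---|---|
| 1/2 | 1542 × 1/2 = 771 | 42% |
| 2/3 | 1542 × 2/3 = 1028 | 56% |
| 3/4 | 1542 × 3/4 ≈ 1157 | 63% |

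These are planned patients whose regimen would be known even if this study's own codes stayed locked. Incomplete rollover lowers the counts, and some of these patients may have finished by the unblinding date.

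**The case against.** **The 3.8.2 assurance may be meant only for bioanalytical staff.** It follows the paragraph on bioanalysis, and 3.7 exempts those staff from the blind. On that reading the assurance would be true. But it identifies the people concerned by reference to 3.7, and 3.7 also names the sponsor. The text does not support the narrower reading as it stands.

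**This study's codes are held in Clinical Supply Chain until analysis (Protocol 3.8.1).** That protects new patients and former placebo patients. It does not protect active rollovers, whose pivotal code is enough.

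**Section 7.1.5.3.1 says that people directly involved stay blinded.** It does, but nothing separates an unblinded sponsor group from the staff who review adverse events.

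**Some unblinding is needed for the licence application.** This is fair. The interim cut needs unblinded people to prepare it, but does not by itself require the medical monitor or the serious-adverse-event assessors to be unblinded.

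**The effect on the results is limited.** This stands. A reader might infer that the blind fails for the primary safety endpoint as a whole, or that the comparison of related events between regimens would be biased. The documents do not support either:

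- Section 3.7 does not unblind investigators or patients.
- Relationship, severity and seriousness are recorded as the investigator judges them (7.1.2), and the related-event tables use the investigator's call (9.7.2, SAP 7.3).
- Withdrawal for an adverse event is mainly at the investigator's discretion (7.1.7).
- No per-protocol set exists, so keeping or removing a violator does not change who is in the safety set.
- All arms are active and no inferential analysis is planned (9.6, SAP 4.4).

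**Conclusion.** The plan is wrong as written. From pivotal unblinding onward, the synopsis statement and the 3.8.2 assurance are untrue at sponsor level. This rests on the current protocol and SAP text and does not depend on the amendment summary.

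The reach is roughly 42% to 63% of the 1842 planned patients through pivotal codes alone, on the assumptions of 1/2 to 3/4 active allocation and full rollover. The unblinding falls mid-study for late rollovers, but how much of their treatment it affects cannot be fixed without a date.

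The exposure is confined to sponsor-level causality of serious adverse events, expectedness, medical monitoring, and withdrawal or retention decisions. These could be influenced; nothing in the documents shows that they would be. Site-recorded events and investigator judgements remain blinded. The point should be corrected, but it does not undermine the safety data as a whole.

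**What to change.** In Protocol 3.7 and SAP 2.4.2, replace the unblinding sentence. State that at pivotal unblinding, treatment codes go only to the statistician and the staff preparing the interim cut for the licence application. State also that the clinical project physician or medical monitor, the serious-adverse-event assessors, the violation reviewers and site-facing staff stay blinded to patient-level codes until this study's database lock. This must include pivotal codes for patients still in this study. Align the synopsis and 3.8.2, and make 3.8.2 (and its copy in SAP 2.4.2) say which roles it covers.

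If sponsor-wide unblinding is intended or has already happened, correct the synopsis, delete or restrict the 3.8.2 assurance, record the unblinding date, and describe the study as investigator- and patient-blind from that date.

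Splitting the adverse-event tables by onset before and after that date would not help. The split is confounded with time on treatment and drop-out, and it would tabulate judgements by investigators who remain blinded.

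The cost is wording plus role-based access control. The small downside is that the staff kept blinded must wait for patient-level pivotal codes while the submission is prepared.

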3.8. Maintenance of Randomization and Blinding

3.8.1. Randomization

Patient randomization codes will be maintained in a secure location within Teva Clinical Supply Chain. At the time of analysis, when treatment codes are needed, the Teva statistician assigned to the study will make a request to unblind and will receive the unblinded codes.

3.8.2. Blinding/Unblinding

Pharmacokinetic data may be assessed during the study. Personnel responsible for bioanalysis will be provided with the randomization code in order to facilitate the analysis. However, the personnel responsible for bioanalysis will not have access to clinical safety and efficacy data and will provide concentration data to other personnel in a manner that will not identify individual patients (ie, a dummy patient identifier will be linked to an individual patient's concentration data).

For information about personnel who may be aware of treatment assignments, see Section 3.7. These individuals will not be involved in conduct of any study procedures or assessment of any adverse events.

In case of a serious adverse event or pregnancy, or in cases when knowledge of the study drug assignment is needed to make treatment decisions, the investigator may unblind the patient's drug assignment as deemed necessary, mainly in emergency situations. Individual treatment codes, indicating the treatment randomization for each randomized patient, will be available to the investigator(s) and/or pharmacist(s) at the study center via the IRT, both via telephone and internet. If possible, the sponsor should be notified of the event prior to breaking of the code. If this is not possible, the sponsor should be notified immediately afterwards, and the patient's drug code assignment should not be revealed. Breaking of the treatment code can always be performed by the site without prior approval by the sponsor.

When a blind is broken, the patient will be withdrawn from the study, and the event will be recorded onto the CRF. The circumstances leading to the breaking of the code should be fully documented in the investigator's study files and in the patient's source documentation. Treatment assignment should not be recorded in any study documents or source documents.

In blinded studies, for adverse events that are defined as suspected unexpected serious adverse reaction (SUSAR) (ie, reasonable possibility; see Section 7.1.4), Global Patient Safety & Pharmacovigilance may independently request that the treatment code be revealed (on a case-by-case basis) to comply with regulatory requirements. The report will be provided in an unblinded manner for regulatory submission. If this occurs, blinding will be maintained for the investigator and for other personnel involved in the conduct, analysis, and reporting of the data.

